6.0 STUDY PRODUCTS

6.1 Allogeneic Umbilical Cord Blood

Allogeneic unrelated donor CB units utilized for this trial will be obtained from the Carolinas Cord Blood Bank, an FDA licensed Public Cord Blood Bank at Duke University Medical Center. However, if a qualifying CB unit cannot be found from the Carolinas Cord Blood Bank, another accredited bank may be used to locate a matching CB unit with the matching criteria. CB donors must be eligible for donation to a public cord blood bank for allogeneic use. Donor eligibility screening via questionnaires is performed in accordance with CFR 1271.75 and infectious disease testing is performed in accordance

with CFR 1271.80 and 1271.85. The unit must also have an appropriate degree of HLA matching and meet product specifications as detailed below.

HLA Matching

All potential study participants will undergo high resolution HLA typing at HLA-A, B, and HLA-DRB1 via blood or buccal swab. Patients receiving allogeneic CB will have HLA typing performed on two separate samples for confirmation. Allogeneic units that are potential matches will initially be identified from a search of the Carolinas Cord Blood Bank, or another accredited bank. The best available HLA-matched (\geq 4/6), using intermediate level matching at HLA Class I A and B and high resolution-allele level matching at HLA Class II, DRB1, CB unit with a pre-cryopreservation nucleated cell dose \geq 12 x 10⁷ cells/kg will be selected (we target CB units that are at least 12 x 10⁷/kg, however, we will accept units that are \geq 10 x 10⁷/kg.) Once a unit is selected, HLA typing will be used to confirm the original HLA typing and to select the best matching unit. When possible, at least 1 match at each HLA loci will be prioritized. A CB unit must be at least 4/6 HLA-matched with the patient.

ABO/Rh Compatibility

Recipients' ABO/Rh blood typing will be obtained. CB units will not be selected based on ABO typing. However, an Rh negative CB unit will be selected for Rh negative female participants to avoid Rh sensitization in young females.

CB Unit Characterization

Results of initial testing at the cord blood bank must include a pre-cryopreservation TNCC, viability and sterility culture. Pre-cryopreservation TNCC must be $\geq 12 \times 10^7$ /kg (we will accept units that are $\geq 10 \times 10^7$ /kg) to target administration of 10×10^7 cells/kg post thaw, sterility cultures must have been negative, total viability must have been $\geq 85\%$, and CD34+ cell viability (if performed) must have been $\geq 70\%$.

A test vial or segment must be available from each CB unit for potency testing and confirmatory HLA typing. The segment will be detached from the candidate unit and tested for potency and identity (HLA-confirmatory typing) per Standard Operating Procedures in the CCBB at Duke. Units will be deemed acceptable for the trial if viability of the CD45 cell population is ≥40% and viability of the CD34 cell population is ≥70%. CFU growth, expression of aldehydehydrogenase and CD34 will be described but will not be a specification for study enrollment.

Prior to the patients' arrival, their designated CB unit will be transferred from the Carolinas Cord Blood Bank (or other accredited bank) to the Duke STCL, located in the same building, where it will be stored in a liquid nitrogen freezer until the day of infusion. On the infusion day, the CB will be thawed and washed in dextran/albumin and resuspended in an appropriate volume based on recipient weight for administration to the patient the standard fashion¹¹⁵ per SOP STCL-PROC-036. At the time of thawing, standard studies listed (see table) will be performed. Only TNCC is utilized for release. A maximum dose of 10x10⁷ TNC/kg will be prepared for infusion in a syringe or bag and infused over 2-25 minutes.

Pos	t-Thaw	Cord	Blood	Unit	Testing
-----	--------	------	-------	------	---------

Test	Specifications
Total Nucleated Cell Count (TNCC)	Report; used to calculate final dose
Viability	Report
Viability of the CD34+ population*	≥70%
Viability of the CD45+ population	≥40%
Sterility**	No Growth
Colony Forming Unit (CFU) growth	Report
ALDH ^{br} as a percentage of CD45+ cells	Report

*Viability of the CD34+ cells post-thaw was previously tested on a segment and required to meet the specification of ≥70%. Therefore, for the clinical product, we will report but not use the post-thaw viability as a release criteria.

**If a positive culture is obtained after product administration, a plan is put into effect to notify the clinical and study teams and treat the patient if indicated.

6.2 Human Umbilical Cord Tissue-derived Mesenchymal Stromal Cells (hCT-MSC)

hCT-MSCs are a product of allogeneic cells manufactured from digested umbilical cord tissue that is expanded in culture, cryopreserved and banked (complete composition and manufacturing details available in IND 17313). hCT-MSCs are manufactured in the Duke CT2 GMP cell manufacturing lab from umbilical cord tissue donated to the Carolinas Cord Blood Bank, an FDA-licensed, FACT-accredited, public cord blood bank at Duke University Medical Center, after written informed consent from the donor baby's mother. Cord tissue is harvested from the placentas of male babies delivered by elective C-section after a normal, full-term pregnancy. Donor screening questionnaires are completed by the maternal donor, and maternal blood is tested for communicable diseases by the CLIA-certified donor screening laboratory in Charlotte, NC. Donors must be eligible for donation to a public cord blood bank for allogeneic use. After delivery of the placenta and cord, the cord blood is aseptically drained from the placenta. Then the cord is dried and cleaned with chloropreps, separated from the base of the placenta, placed in a sterile bottle containing Plasmalyte A, and transported to the Robertson CT2 GMP cell processing laboratory at room temperature in a validated container.

In the clean room manufacturing suite, in a biosafety cabinet, the cord tissue is removed from the media, placed in sterile dishes, cut into small pieces and then minced and digested in the Miltenyi Biotec GentleMacs Octo Dissociator with GMP-grade enzymes: hyaluronidase, DNase, collagenase, papain. The resultant cell suspension is placed in culture in Prime XV MSC Expansion XSFM (Irvine Scientific) media with 1% platelet lysate and grown to confluence (~7-14 days) to establish the P0 culture. To establish the master cell bank, P0 is harvested and cryopreserved in cryovials with Cryostor 10 media (BioLife), and stored in the vapor phase of liquid nitrogen. P1 and P2 cultures are grown under similar conditions, in HYPERFlasks or HYPERStacks without platelet lysate, as needed to create the working cell bank and product for administration, respectively. Cells from P1 and P2 are removed from plastic cultureware using TrypLE (Gibco). The final product is derived from the P2 cultures which are harvested into
plasmalyte with 5% human serum albumin, washed and cryopreserved in compartment cryobags containing 50-100 million cells in a final concentration of 10% DMSO with dextran (Akron Scientific). On the day of administration, one compartment is thawed, diluted in 10-40 mLs of plasmalyte IV solution, placed in a syringe or bag and transported to the bedside for administration over 30-60 minutes.

At each passage, the cell product is characterized by assessing cell surface phenotype by flow cytometry and functional assays via T-cell proliferation and organotypic models of microglial activation. Each lot, prior to cryopreservation of P2, will also be tested for sterility, endotoxin and mycoplasma and these tests must meet specifications. For dosing, release testing after thaw and dilution will include TNCC and viability via cellometer. Patients will be dosed with 2x10⁶ hCT-MSCs/kg based on the post thaw count.

Process and Final Formulation

hCT-MSC is manufactured from a single umbilical cord tissue in a series of three steps that generate a master cell bank, a working cell bank, and the study product. The product for each step is cryopreserved in a controlled rate freezer and stored in the vapor phase of liquid nitrogen. At P2, a representative cryobag is thawed and qualified prior to the treatment of any patients with that lot of product. Testing for product release includes total nucleated cell count, viability, phenotype, functional assays, endotoxin, mycoplasma, gram stain and sterility. Each lot of cells is also tested for adventitial viruses prior to cryopreservation.

On the day of treatment, cells are thawed per SOP STCLAOP-028 JA2 and then diluted in 10-40 mLs of plasmalyte A + 5% human serum albumin (HSA). An aliquot is removed for cell count, viability, and sterility culture. If the cells are \geq 70% viable, the final product volume is adjusted to deliver 2x10⁶ cells/kg to the study subject. The cells are delivered to the bedside in a syringe containing plasmalyte A, 5% HSA, and residual DMSO. Any removed cell suspension is inoculated into aerobic and anaerobic culture bottles for sterility testing. The cells have a four-hour expiry at room temperature post thaw.

The hCT-MSC final product will be released conditionally for administration to the patient after testing a post thaw cell count and viability. Final release will occur after the 14-day sterility culture period for the study product. In the event that a sterility culture turns positive after administration of the product, the organism will be identified and antibiotic sensitivities performed. The patient's family will be contacted to determine if they are symptomatic (i.e. fever or other signs of infection). Asymptomatic patients will be observed but will not be treated with antibiotics. Symptomatic patients will be evaluated and treated accordingly, with blood cultures and antibiotics as appropriate. All patients receiving a product with subsequent positive sterility test will be followed with daily contact by a study nurse for 14 days after the positive sterility test is noted.

6.3 Donor Screening for CB and hCT-MSC

Donor screening and testing is performed per Carolinas Cord Blood Bank standard operating procedures to meet all requirements in 21CFR Part 1271. The screening and testing is current with recommendations and is approved by the FDA under biological license number 1870. Maternal donors of umbilical cord blood are screened and tested for HIV-1, HIV-2, HIV-O, hepatitis B virus (HBV, surface antigen and core antibody), hepatitis C virus (HCV) antibody, Treponema pallidum (syphilis), Creutzfelds-Jakob Disease (CJD, screening only), Chagas Disease, human T-lymphotropic virus types 1

and 2 (HTLV-1, HTLV-2) and total antibodies against CMV. Nucleic acid testing for HIV-1/2/O, HBV, West Nile Virus and HCV are also performed on maternal blood. Screening for Zika virus may also be performed.

Because the cord tissue used for this study will be obtained from donors consented for cord blood donation to the Carolinas Cord Blood Bank, they will undergo donor screening and infectious disease testing per Carolinas Cord Blood Bank standard operating procedures. The cord blood-associated maternal samples and cord tissue MSC samples will be retained as reference samples for future testing as part of this study.

6.4 Packaging of Study Products

All cellular products receive a unique identification number (ISBT Demand 128 bar code) to ensure product integrity and maintain chain of custody. The clinical site or cord blood bank assigns an ISBT Demand 128 bar code label to the CB unit or hCT-MSC product, which is placed on the product bag/syringe directly or via tie tag. Products are transported from the STCL to the infusion site in a validated cooler by a trained courier.

6.5 Administration of Study Product

Patients will be arrive in clinic on the morning of their scheduled infusion. A peripheral IV will be placed either by an anesthesiologist, clinical staff or study staff and premedication with Benadryl 0.5mg/kg/dose IV and Solumedrol 0.5-1mg/kg IV will be administered. Allogeneic CB products will be administered intravenously over 5 to 25 minutes under direct physician supervision. hCT-MSC products will be administered intravenously over 30-60 minutes under direct supervision. Vital signs (heart rate, blood pressure, temperature, respiratory rate) will be checked upon arrival to the clinic and as clinically indicated. Pulse oximetry will be monitored continuously throughout the infusion and for at least 5 minutes post infusion. Patients will be hydrated with standard intravenous fluids as tolerated and observed for at least one hour post infusion.

6.6 Safety Follow-up

On Day 1 following the infusion, the participant will be seen by study staff to assess for any infusion related adverse reactions or complications. At ~2 weeks post-infusion, a member of the study team will contact the parent or guardian via phone or email to assess patient status and any adverse events. In-person safety assessments will occur at each study visit. In addition, a questionnaire (see Appendix 1) will be administered at 6, 12, and 24 months post baseline visit to assess for serious adverse events.

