4.0 STUDY DESIGN

4.1 General Design

This study is a phase I/II, prospective, randomized, open-label trial designed to determine the effect size of change in GMFM-66 score in subjects treated with hCT-MSC or allogeneic CB and assess the safety of repeated doses of hCT-MSC in children with cerebral palsy. Children ages 2-5 years with cerebral palsy due to hypoxic ischemic encephalopathy, stroke, or periventricular leukomalacia may be eligible to participate. All participants will ultimately be treated with an allogeneic cell product at some point during the study. Participants will be randomized to one of three arms: (1) the "AlloCB" arm will receive one allogeneic CB infusion at the baseline visit; (2) the "MSC" arm will receive three hCT-MSC infusions, one each at baseline, three months, and six months; (3) the "natural history" arm will not receive an infusion at baseline but will receive an allogeneic CB infusion at 12 months. Motor outcome measures will be assessed at baseline, six-months, and one-year time points. Safety will be evaluated at each infusion visit and remotely for an additional 12 months after the final visit. Duration of study participation will be 24 months from the time of baseline visit. Randomization to treatment arms will be stratified by GMFCS level at study entry and etiology of CP (Stroke vs. Other).

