4.3 Study Endpoints

Primary Endpoint:

The primary endpoint is the difference between a participant's observed and expected changes in GMFM-66 score 12 months after the initial study infusion. Interval estimates will be reported separately for the hCT-MSC, AlloCB, and Natural History arms. Expected GMFM-66 scores at 12 months will be calculated based on the participant's baseline age, GMFCS level, and GMFM-66 score at study entry using published reference percentiles.⁶⁴

Secondary Endpoints:

The secondary endpoint is the number of adverse events occurring over the 12-month period post-infusion with hCT-MSC or AlloCB.

Exploratory Analyses:

- Observed GMFM-66 score at baseline, 6, and 12 months
- Change in the Peabody Developmental Motor Scale-2 (PDMS-2) score at 6 and 12 months.
- Change in normalized total brain connectivity, as measured by brain MRI with DTI, from baseline to 12 months.
- Change in functional and quality of life measures at 6 and 12 months.

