7.4 Study Product Infusion

On the day of infusion, CB cells or hCT-MSC product will be prepared by the STCL and provided for infusion of the patient in the outpatient clinic under the supervision of the study team and Pediatric Blood and Marrow Transplant Program staff. A peripheral IV will be placed by clinical staff, anesthesia or a member of the study team. Prior to the study infusion, premedications (Benadryl and Solumedrol) will be administered. CB cells will have a four-hour expiry at room temperature post-thaw.

Allo CB infusion will be given over approximately 5-25 minutes and hCT-MSC infusions over 30-60 minutes using standard practices. The child will receive 1-1.5x maintenance

IV fluids as described below and be observed in the clinic for a minimum of one hour after the infusion. Patients will be discharged from clinic after at least one hour providing all vital signs are at their baseline and they are awake and asymptomatic with no evidence of toxicity. Patients will be evaluated by study staff the day after the infusion to assess for any infusion-related adverse reactions or complications. A phone call to parents/guardians by study staff to assess safety of the infusion will be conducted two weeks after the infusion.

Maintenance IV Fluid Rate (Holliday-Segar Method from Harriet Lane Handbook)Body weight:mL/kg per day1st 10 kg100divided by 24hr/day2nd 10 kg50divided by 24 hr/dayeach add'l kg20divided by 24 hr/day

If a patient has evidence of illness on the day of planned infusion, including but not limited to fever >38.5° C, vomiting, diarrhea, or respiratory distress, the infusion will be postponed.

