7.9 Required Evaluations

	Time Points#					
	Screening	Baseline	3 months	6 months	12 months	24 months
All Participants						
CBCD*, CMP*, Type & Screen*, Patient HLA typing	Х					
Patient DNA sample for chimerism		Х				
CBCD*, CMP*, Type & Screen*, Direct Coombs, HLA Antibody Screen (PRA), Immune Reconstitution Panel, Humoral Immune Profile		х			х	
Motor Assessments (GMFM-66, PDMS-2)		Х		Х	Х	
Brain MRI^		Х			Х	
Functional Assessment (PEDI-CAT)		Х		Х	Х	
Safety Assessment – remote						Х
AlloCB Participants						
CBU potency; HLA confirmatory typing	Х					
History & Physical		Х		Х	Х	
Donor Referral Panel		Х				
CBU: TNCC, viable CD34 ⁺ count, CFU, sterility culture, donor DNA sample for chimerism		х				
Safety Assessment – in-person, day after infusion		Х				
Natural History Participants						
CBU potency; HLA confirmatory typing	Х					
History & Physical		Х		Х	Х	
Donor Referral Panel					Х	
CBU: TNCC, viable CD34 ⁺ count, CFU, sterility culture, donor DNA sample for chimerism					Х	
Safety Assessment – in-person, day after infusion					Х	
MSC Participants						
History & Physical		Х	Х	Х	Х	
Donor Referral Panel		Х				
CBCD, CMP			Х	Х		
Safety Assessment – in-person, day after infusion		Х	Х	Х		
*CBCD and CMP may be obtained at baseline or within 6 month ^Brain MRI will be performed on patients with eligible screening		nt				

*Safety and return assessments should be performed within a month of the indicated time point.

Abbreviations: CBCD-Complete Blood Count and Differential, CMP-Complete Metabolic Panel, HLA-Human Leukocyte Antigen, GMFM-66-Gross Motor Function Measure-66, PDMS-2-Peabody Developmental Motor Scale-2, MRI-Magnetic Resonance Imaging, CBU-Cord Blood Unit, TNCC-Total Nucleated Cell Count, CFU-Colony Forming Units

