8.0 STATISTICAL CONSIDERATIONS

8.1 Study Design

This study is a phase I/II, prospective, randomized, open-label trial designed to provide interval estimates of the 12-month change in motor function after treatment with AlloCB and hCT-MSC, provide additional data to the clinical trials community on the natural history of the motor function in CP over short-term (less than 1 year) time periods relevant to conduct of clinical trials, and assess the safety of repeated doses of hCT-MSC and a single dose of AlloCB in children with cerebral palsy.

Children ages 2-5 years with cerebral palsy due to hypoxic ischemic encephalopathy, stroke, or periventricular leukomalacia will be eligible to participate. All participants will ultimately be treated with an allogeneic cell product at some point during the study. Participants will be randomized (1:1:1) to one of three arms: (1) the "AlloCB" arm will receive one allogeneic CB infusion at the baseline visit; (2) the "MSC" arm will receive three hCT-MSC infusions, one each at baseline, three months, and six months; the "natural history" arm will not receive an infusion at baseline but will receive an allogeneic CB infusion at 12 months. The occurrence of adverse events will be evaluated at 3, 6, 12, and 24 months post-randomization in all participants. Motor function outcome measures will be assessed at baseline, six-months, and one-year time points in all participants. Duration of study participation will be 24 months from the time of the baseline visit. Randomization will be stratified by GMFCS Level (I/II or III/IV) and etiology of CP (Stroke vs. Other).

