8.3 Study Duration

Each subject's participation in the study will be 24 months, with clinic visits occurring during the first 12 months and a remote safety assessment at 24 months. Given that accrual will take up to 15 months it is estimated that the remote safety assessment will be conducted on that last patient 39 months (3.25 years) after the study opens.

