9.5 Stopping Guidelines

The following stopping guidelines will be monitored during the duration of the study. The stopping guidelines will be monitored by the CRO, The EMMES Corporation, and are to be used to indicate boundaries requiring discussion by the investigators and DSMB. The study will be stopped for a safety review if:

- Any subject experiences a grade 4-5 infusion reactions within 24 hours of infusion; OR
- Two or more grade 4-5 adverse events determined to be temporally related by the medical safety monitor and/or the DSMB occur; OR
- Any subject experiences a blood stream infection within 6 months of infusion; OR
- Any death.

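### Natural History children have no dated safety contact between about 2 weeks and 12 months after their month-12 cord blood infusion; one remote questionnaire at month 18 would close most of the gap cheaply.

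*Combined protocol and SAP*

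**What the plan says.** Section 4.1 gives the Natural History arm its cord blood infusion at month 12. Two safety contacts are timed from each infusion: a day-after visit (6.6) and a 2-week contact, which 7.4 describes as follows: "A phone call to parents/guardians by study staff to assess safety of the infusion will be conducted two weeks after the infusion".

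The later contacts run on the baseline or randomization clock:
- The questionnaire in 6.6 "will be administered at 6, 12, and 24 months post baseline visit to assess for serious adverse events".
- Section 8.1 states: "The occurrence of adverse events will be evaluated at 3, 6, 12, and 24 months post-randomization in all participants".
- Section 8.3 describes participation as 24 months, "with clinic visits occurring during the first 12 months and a remote safety assessment at 24 months".
- The footnote to 7.9 sets the tolerance: "Safety and return assessments should be performed within a month of the indicated time point".

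Section 4.1 adds: "Safety will be evaluated at each infusion visit and remotely for an additional 12 months after the final visit". It gives no interim date.

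Two safety rules run on the infusion clock. The secondary endpoint (4.3) is the "number of adverse events occurring over the 12-month period post-infusion with hCT-MSC or AlloCB", analysed as treated in everyone infused (8.6.1). One stopping guideline (9.5) reads: "Any subject experiences a blood stream infection within 6 months of infusion".

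**The concern.** The schedule suits children infused at baseline. When the infusion moves to month 12, most of the follow-up dates have already passed. Half of the planned cord blood recipients then go from week 2 to month 12 after infusion with no scheduled enquiry. Events in that interval reach the study only if the family volunteers them, or by recall at month 24.

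Two things are at stake:
- **Recognition.** A blood stream infection that counts under the 6-month guideline in 9.5 could come to light about 12 months after infusion, while other Natural History children are still being infused.
- **Ascertainment.** The 12-month adverse event count for cord blood combines children asked in person at 6 and 12 months with children asked once, remotely, at 12 months. Section 8.6.4 reports by treatment received and does not separate them.

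**Working it through.** **Plan's own figures.** Section 8.5 sets 30 per group and gives the probability of seeing at least one event as 1 − (1 − p)^30. For p = 1%, 5% and 10% this gives 26.0%, 78.5% and 95.8%, as printed. These figures assume that an event which occurs is also recorded. With 1:1:1 allocation, planned cord blood recipients are 30 AlloCB + 30 Natural History = 60, so Natural History is half.

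**Contacts in the 12 months after cord blood** (time since infusion; 2 weeks taken as 0.5 month)

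| | AlloCB (infused at month 0) | Natural History (infused at month 12) |
|---|---|---|
| Day 1 | in person | in person |
| About 2 weeks | phone or email | phone or email |
| 6 months | in person + questionnaire (study month 6) | none (would be study month 18) |
| 12 months | in person + questionnaire (study month 12) | remote (study month 24) |

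The month-3 evaluation in 8.1 is not counted for AlloCB, because 7.9 schedules no AlloCB assessment then.

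**Longest interval without a dated contact**
- Natural History: 12 − 0.5 = 11.5 months (about 10.5 to 12.5 with the one-month tolerance).
- AlloCB: max(6 − 0.5, 12 − 6) = 6 months.
- Natural History with month 18 added: max(5.5, 6) = 6 months.

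**Delay for an event that is not spontaneously reported**
- Greatest nominal delay relative to AlloCB: 12 − 6 = 6 months, for events before month 6. For events in months 6 to 12 the next contact is month 12 in both arms, so the difference is zero.
- Assuming event times uniform between 2 weeks and 12 months, the mean time from event to next contact is 11.5/2 ≈ 5.8 months now. With month 18 added it is (5.5²/2 + 6²/2)/11.5 ≈ 2.9 months.

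**Status at the secondary-endpoint analysis.** Section 8.6.2 places this at the last patient's month 12. Let A be the accrual period, with even accrual. A Natural History child enrolled at time t is infused at t + 12 and the analysis is at A + 12, so post-infusion follow-up is A − t. The share with at least c months is max(0, (A − c)/A). Section 8.2 gives both 8–12 enrolled per month (90/12 = 7.5 to 90/8 = 11.25 months) and 12–15 months of accrual.

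| A (months) | Reached month 18 (c = 6) | Reached month 24 (c = 12) |
|---|---|---|
| 7.5 | 1.5/7.5 = 20%, 6 of 30 | 0 |
| 11.25 | 5.25/11.25 = 46.7%, 14 of 30 | 0 |
| 12 | 6/12 = 50%, 15 of 30 | 0 |
| 15 | 9/15 = 60%, 18 of 30 | 3/15 = 20%, 6 of 30 |

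**Children infused in the meantime.** Natural History infusions run from study month 12 to 12 + A. Take an unreported event in the first child infused. Between that child's month-18 and month-24 contacts, the number of further Natural History children infused is 30 × min(6, A − 6)/A. For A = 7.5, 11.25, 12 and 15 this gives 6, 14, 15 and 12. This is the most favourable case for the extra contact; the number shrinks for children infused later.

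**The case against.** The strongest reply is that no part of the 12-month window is formally uncovered. The month-24 contact falls at its end. Appendix 1 asks about events since the last study visit, including hospitalization, serious infection and any other health problem. Section 9.2 requires every reported event to be recorded from enrollment, the post-thaw sterility culture triggers notification if positive (6.1), and 8.6.2 plans a 24-month safety update covering all these children. That stands: the weakness is late, recall-dependent ascertainment, not absent follow-up.

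Three further points also stand in part:
- A month-18 questionnaire looks back over the 6-month stopping window and does not monitor within it. The AlloCB month-6 visit, at the edge of the same window, does no better.
- Six months is the maximum delay. Averaged over uniform event times, the difference is about 2.9 months.
- The secondary objective in 3.0 concerns repeated hCT-MSC doses, the detection probabilities in 8.5 are met by the 30 AlloCB children alone, and the adverse event analysis is descriptive. No planned test is biased.

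Other replies carry less weight. Every arm has a remote interval from month 12 to 24, but only for Natural History does it begin at dosing. Section 7.1 places the remote assessment 24 months after infusion. Taken literally that is month 36 for this arm, which contradicts the 24-month participation in 4.1 and 8.3. The 7.5-month accrual case is the extreme reading of 8.2; at 12–15 months the month-18 contact would be reached by 15–18 of 30. The flow chart in 4.2 could not be read, but 7.9, 8.1 and 8.3 make an unlisted month-18 contact unlikely.

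**Conclusion.** The point holds as a cheap improvement to the safety schedule, not as a flaw that threatens the trial. After week 2, Natural History children have one dated contact in the 12 months after cord blood, and it is remote; AlloCB children have two, both in person. The longest gap is about 11.5 months against 6, for up to 30 of 60 planned recipients (fewer if children leave before month 12). The practical consequences are recognition of an unreported event up to about 6 months later, and uneven ascertainment within the as-treated cord blood group. The schedule facts come directly from the protocol. The counts at the analysis date (0–6 of 30 at month 24, about 6–18 of 30 at month 18) rest on even accrual over 7.5 to 15 months, and the average delay rests on uniform event times.

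**What to change.** - In 6.6, 7.9 and 8.1, add one remote Appendix 1 questionnaire for Natural History children about 6 months after their infusion (study month 18). Staff should record the onset date of any reported infection, so that the 6-month guideline in 9.5 can be applied.
- In 8.6.4, report post-infusion adverse events for the AlloCB arm and for Natural History children separately before any pooling.
- In 7.1, correct the timing of the remote assessment to 24 months after baseline, to agree with 4.1, 6.6 and 8.3.

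The cost is one phone or email questionnaire for up to 30 families, a small amount of coordinator time and one extra table column. No visit, staff or procedure is added, and participation stays at 24 months. Because the form looks back to the last study visit, the month-18 and month-24 answers may repeat the same event, so duplicates need reconciling.
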